4.4.2. Exclusion criteria

Patients with allergies to any of the drugs used in the trial

Patients with chronic pain

Patients who are diagnosed with CNS diseases, like psychiatric diseases or epilepsy([46](#))

Patients who are hypertensive and taking beta-blockers, as well as those who have preoperative bradycardia, hypotension, or any type of heart block([47](#))

Patients weighing less than 40 kg or obese patients (BMI > 35 kg/m²)([12](#))

Patients with a history of smoking

Patients who are scheduled for postoperative mechanical ventilation

4.5. Sampling procedure and sample size

The sample size (N) was calculated by the formula for a continuous outcome variable with equal sample sizes in both groups, $n = 2[(Z_{\alpha}/2 + Z(1-\beta))^2 * \sigma^2]/(d^2)$ by G-power calculator. We assumed: significance level ($Z_{\alpha}/2$) = 0.05, taken 1.96, and power of study $Z(1-\beta)$ = 0.80, taken 0.84; σ^2 is the standard deviation taken from a previous study in South Korea⁴⁸, which is 1.9. Assuming a medium effect size in the OFA group compared to those receiving fentanyl is clinically significant, the calculated sample size for each group is 31, resulting in 62 participants in both groups. To account for potential contingencies, an additional 10% is added to the final sample size, resulting in 70 participants.

4.6. Random sequence generation

The eligible participants presenting for gynecologic surgery at both study areas during the study period will be selected. Participants will be allocated to study groups by a computer-generated random allocation sequence number created by an independent anesthetist with a 1:1 allocation to the treatment group (T) and control group (C) the night before surgery.

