SBP	Systolic Blood Pressure
SNNPR	Southern Nations Nationalities and Peoples Region.

III. Executive Summary

Background: Long-term use of opioids has been linked to various side effects and decreased patient satisfaction after anesthesia. A combination of drugs with opioid was used for intraoperative analgesia. Multiple drugs, by avoiding opioids, was a new opinion suggested. Opioid-free anesthesia with a combination of drugs is a new idea to avoid opioid from postoperative analgesia.

Objective: To determine the effectiveness of low-dose ketamine and intravenous lidocaine versus fentanyl for postoperative pain in patients undergoing elective gynecologic surgery under general anesthesia at Dilla University Teaching Hospital and Hawassa University Comprehensive and Specialized Hospital from April 10 to October 10, 2023.

Methodology: A multicenter, randomized, controlled, single-blinded superiority trial will be conducted with 70 adult patients undergoing elective gynecologic surgery under general anesthesia. Randomization will be done by a computer-generated random allocation sequence in equal ratios to the treatment group ($T = 35$) and the control group ($C = 35$). The primary dependent variable is the pain severity measured by a visual analog scale postoperatively at discharge from the post-anesthesia care unit, 6th hour, 12th hour, and 24th hour, and the secondary outcomes are postoperative nausea and vomiting, postoperative analgesia request, and intraoperative cardiac adverse events. Student's t-test, analysis of variance, and chi-square test will be used for data analysis. A p-value of less than 0.05 was determined as statistically significant.

Work plan and budgeting: - study will be conducted from April 10, 2023, to October 10, 2023, with a cost of 41625 ETB.

1. Introduction

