4.2. Study design

A multi-centered, randomized, controlled, single-blinded trial will be conducted at Dilla University General and Teaching Hospital and Hawassa University Comprehensive and Specialized Hospital.

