4.10. Data collection procedures

After getting ethical clearance from the Dilla University College of Health Sciences and Medicine ethical review board, a structured questionnaire will be formed and translated into the respective languages by the principal investigator (PI). Two BSC anesthetists involved in patient management will be selected at both study areas and trained in the overall process of participant handling and data collection.

During the preoperative period

Patients undergoing gynecologic operations during the study period will be assessed and told about the study process and anesthetic the day before the surgery. The patient will receive maintenance fluid, had bilateral peripheral IV lines secured, and was NPO the night before surgery. On the morning of the procedure, both a standard informed consent form for the procedure and a separate consent form for the study will be checked and available.

The availability and functionality of the bilateral IV line, and NPO status will be checked, and prophylactic drugs will be given. Standard preoperative questionnaires will be used, and data will be collected through patient responses and medical records, such as patient monitoring and charts.

At intraoperative period

Routine ASA monitoring will be checked and applied for patients in both groups when the patient presented to the OR. The functionality and availability of the bilateral IV line and urinary catheter will be rechecked. Propofol (3 mg/kg) will be given to induce anesthesia after the patient had been pre-oxygenated for both groups. An intravenous bolus of 0.5 mg/kg of ketamine during the induction phase for patients in the treatment group, then a continuous infusion of 0.2 mg/kg/hr. Of ketamine. A bolus of 1.5 mg/kg will be given before induction, and the same dose of lidocaine will be administered every 15 to 20 minutes after induction of anesthesia until the start of skin closure.

Patients in the control group will be induced with fentanyl 2 μ g/kg given during induction of anesthesia with propofol 3mg/kg. 0.5 μ g /kg of fentanyl will be given every 20-30 minutes up to the start of skin closure.

Intubation will be performed after administering 1.5–2 mg/kg IV suxamethonium. Inhalational anesthetics as availabilities (Isoflurane 0.75–2% and Halothane 1%_ 2%) were opened after the position of the ETT was confirmed, and Dexamethasone 0.15mg/kg IV bolus will be given after securing the ETT.

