Anesthesia will be maintained with inhalational agents according to the patient's tidal volume of 6–8 ml/kg adjusted to maintain oxygen saturation >95% with 3- 4 ml 100% oxygen flow, and end-tidal CO₂ between 32 and 45 mmHg. Muscle relaxation will be maintained with vecuronium 0.8 mg/kg. Intraoperative anesthesia depth will be assessed by clinical signs as well as by patient monitoring. Estimated intraoperative blood loss will be supplied with ringer lactate or normal saline.

The intraoperative participants' data will be collected from the anesthesia record chart and patient monitoring. Intraoperative hemodynamic variables will be collected every 10 minutes. Intraoperative cardiac adverse events such as intraoperative bradycardia (pulse rate less than 50 bpm), tachycardia (PR greater than 100 bpm), hypertension, and hypotension we diagnosed and managed as per institutional protocol. Intraoperative nausea or vomiting in both groups will also be managed as an institutional protocol.

When the surgeon begins skin closure, the inhalational agent will be turned off. A pre-prepared reversal agent bolus (neostigmine 0.05 mg/kg with atropine 0.02 mg/kg IV) was administered for patients given long-acting muscle relaxants after checking the adequacy of spontaneous ventilation, adequate movement of the respiratory bag, oxygen saturation >95percentage and ETCO₂ between 32 and 45 mmHg after the skin is closed.

During the postoperative period

The postoperative pain severity will be assessed by the validated VAS starting from the patient's discharge from PACU to 24 hours postoperatively. Data will be collected at discharge from PACU, at 6 hours, 12 hours, and 24 hours postoperatively. Analgesia request at postoperative times will be recorded as the patient's request for analgesia according to the VAS score. PONV data will be collected from the time of arrival at PACU at 6 hours, 12 hours, and 24 hours postoperatively according to the patient's signs and symptoms.

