4.12. Data Processing and Analysis Procedure

After every data collection night, inconsistencies in data collection will be examined and fixed. Epi. Info version 7.2 will used for data entry and Statistical Package for the Social Sciences (SPSS) version 27will be used for data analysis.

The normality of data distributions for quantitative variables will be assessed using the Kolmogorov-Smirnov test and Levene's test will be used to check the homogeneity of variance. The plot of the Box will be used to check outliers. Histograms and visual inspection of individual data will be used to verify the data distribution.

Independent t-tests and ANOVA tests will be used to assess continuous data on pain severity at different postoperative times, and results will be presented as mean plus standard deviation. The categorical data of PONV at different postoperative times will be analyzed by chi-square or Fisher exact test and presented as frequencies, percentages, and a bar chart graphically. P-values of less than 0.05 will be determined as statistically significant.

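### Hospital is handled in neither the allocation nor the analysis of this two-hospital trial, so the hospital mix of the arms is left to chance at a modest cost in precision

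*Combined protocol and SAP*

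**What the plan says.** Section 4.2 sets up a multicentre trial at two hospitals. Section 4.6 takes patients from both ("The eligible participants presenting for gynecologic surgery at both study areas during the study period will be selected") and assigns them by a "computer-generated random allocation sequence number created by an independent anesthetist with a 1:1 allocation". The Executive Summary gives the intended arms as "equal ratios to the treatment group ($T = 35$) and the control group ($C = 35" but not how equality is secured. Section 4.7 adds sealed envelopes without saying how the sequence is divided between the hospitals. Strata, separate lists, blocks and minimisation are mentioned nowhere.

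On the analysis side, hospital is not among the independent variables in section 4.8.2. Section 4.12 compares pain by t-tests and ANOVA with no stated covariate or site factor, and PONV data "will be analyzed by chi-square or Fisher exact test".

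Two items in section 4.10 could vary by site. Intraoperative cardiac events are "we diagnosed and managed as per institutional protocol": bradycardia and tachycardia have numeric limits there, but hypertension and hypotension have none. The volatile agent, isoflurane or halothane, is chosen by supply: "Inhalational anesthetics as availabilities".

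**The concern.** With two hospitals in different cities and 70 patients, one would expect hospital to be balanced in the allocation, adjusted for in the analysis, or both. The plan does neither. If event rates differ between the hospitals, a chance difference in hospital mix adds noise to the treatment comparison. In the one trial that is run, it can also look like part of a treatment effect.

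At stake are the precision of the comparisons, mainly of the binary secondary outcomes, and how far a reader will trust an observed difference if the arms turn out to come from different hospitals in visibly different proportions.

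**Working it through.** **Inputs from the plan.** Two hospitals (section 4.2) and arms of 35 and 35 (Executive Summary). The arm size follows from section 4.5: 31 per group plus 10% is 31 × 1.1 = 34.1, or 31 / 0.9 = 34.4, and both round up to 35.

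**Assumptions.** The documents give neither the patients per hospital nor event rates by hospital. I take 35 patients per hospital (21 and 49 as an alternative) and three pairs of hospital event rates: 30%/50%, 20%/50% and 15%/60%.

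**Step 1: chance difference in hospital mix.** Let X be the number of one hospital's 35 patients in the treatment arm. With totals fixed at 35:35 and no stratification, X is hypergeometric (70 patients, 35 from that hospital, 35 drawn). The difference in hospital share between arms is D = (2X − 35)/35.

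- Var(X) = 35 × ½ × ½ × 35/69 = 4.438, so Var(D) = 4 × 4.438/35² = 0.0145 and SD(D) = 12.0 points.
- P(|D| ≥ 20 points) = 15.1%. D moves in steps of 2/35, and a 21:14 split gives exactly 7/35 = 20 points. The next possible value is 9/35 = 25.7 points, so P(|D| > 20 points) = 5.5%.
- With 21 and 49 patients the two figures are 11.7% and 3.6%.

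**Step 2: what a 20-point difference does.** With rates of 20% and 50%, the arm difference shifts by 0.20 × 0.30 = 6 points. The standard error of the risk difference is 11.4 points (step 3), so this is about half a standard error. For pain, if the hospitals differed by an assumed 1 VAS point, the shift would be 0.20 × 1 = 0.2 points. With the plan's SD of 1.9, 31 per group corresponds to a difference of 1.9 × √(2 × 2.8²/31) = 1.35 points, so 0.2 is about 15% of it.

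**Step 3: variance of the risk difference.**

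- *Plan as written:* (2/35) × mean of p(1 − p) over hospitals + (p₁ − p₂)² × Var(D).
- *Per-hospital lists:* the same, but D can only be ±1/35 (35 is odd, so 18:17 in one hospital and 17:18 in the other), and Var(D) becomes 1/35² = 0.0008.
- *Mantel-Haenszel on the unstratified list:* given X = k, both hospitals carry weight w = k(35 − k)/35 and the variance is [p₁(1 − p₁) + p₂(1 − p₂)]/(4w), averaged over the distribution of X.

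| Assumed rates | As written | Mantel-Haenszel only | Per-hospital lists only |
|---|---|---|---|
| 30% / 50% | 0.01314 + 0.00058 = 0.01372 | 0.01334 (−2.8%) | 0.01318 (−4.0%) |
| 20% / 50% | 0.01171 + 0.00130 = 0.01302 | 0.01189 (−8.7%) | 0.01179 (−9.5%) |
| 15% / 60% | 0.01050 + 0.00293 = 0.01343 | 0.01066 (−20.7%) | 0.01067 (−20.6%) |

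The square root of 0.01302 is 0.114, the standard error used in step 2.

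**Step 4: balance after the change.** Simulating permuted blocks of 4 within each hospital (block size assumed), for hospital splits from 50:50 to 20:80, the mix difference never exceeded 2.3 to 4.6 points, depending on the split.

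**The case against.** The strongest objection is that chance imbalance in a randomized trial is ordinary sampling variation. The test already allows for it, and a shift of half a standard error under an assumed 30-point gap between hospitals is not alarming. That stands: type I error is not inflated, and no effect on the primary outcome is shown beyond an illustration.

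A reader might go on to infer several stronger things that the documents do not support:

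- **That balance can only come from the allocation, because imbalance cannot be separated afterwards.** This is wrong. Mantel-Haenszel on the same unstratified list recovers most or all of the gain (step 3). The larger omission is the missing hospital term in section 4.12.
- **That the anesthetic agent and event diagnosis are set by hospital.** Section 4.10 ties the agent to availability, which may also vary over time within one hospital. Only hypertension and hypotension lack a trial-wide threshold, and PONV has a single definition in section 4.9.
- **That the arms may end far from equal.** Simple randomization of 70 would give exactly 35:35 in only 9.5% of trials, but the stated 35 and 35 suggests that the totals are restricted. Restricting totals does not balance the arms within a hospital; step 1 already assumes it.

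The plan may also intend per-hospital lists without saying so, since both the single sequence and the absence of blocks are read from silence. Finally, small blocks make allocation easier to predict when providers know the groups, as they do under section 4.7. That is a real cost and is addressed in the fix.

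**Conclusion.** The point holds as a cheap improvement, not as a threat to validity. Hospital appears in neither the allocation nor the analysis, so the arms' hospital mix is left to chance and never accounted for. Under the 35-per-hospital assumption, a mix difference of 20 points or more arises in about one trial in seven, and most of that probability is the single outcome of exactly 20 points. The recoverable variance is about 3 to 4% if hospital rates differ by 20 points, 9% at 30 points and 20% at 45 points. Most of it, and in the last case essentially all, comes from the stratified analysis alone. Separate lists add little precision; what they add is visible balance within each hospital. All effect sizes rest on assumed hospital splits and event rates. If the hospitals have similar rates, the gain is close to nil.

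**What to change.** 1. **Section 4.12 (the main gain).** Compare PONV and cardiac events stratified by hospital (Mantel-Haenszel), and include hospital as a factor in the VAS analysis. Add hospital to the variables in section 4.8.2 so that it is recorded for every patient.
2. **Section 4.6.** Have the independent anesthetist generate a separate list for each hospital in randomly permuted blocks of varying size, withhold the block sizes from the providers, and number the envelopes within hospital. If this is already intended, saying so is enough.

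The cost is a few sentences in these sections and one extra computer-generated list, with no added patients, staff or procedures. The downside is slightly more predictable allocation because providers are unblinded; varying and withholding the block sizes limits it. If the sponsor considers even that too much, the first change alone captures most of the precision.

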4.4. Inclusion and exclusion criteria

4.4.1. Inclusion criteria

ASA I and II patients between the ages of 18 and 65 undergoing elective gynecologic surgery at Hawassa University Comprehensive and Specialized Hospital and Dilla University Teaching Hospital under general anesthesia between April 10, 2023, and October 10, 2023, and gave informed consent.

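### Allocating the night before surgery invites avoidable loss between randomisation and induction, and the plan has no rule for patients allocated but never anesthetised

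*Combined protocol and SAP*

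**What the plan says.** Section 4.6 fixes both who is allocated and when. On who: "The eligible participants presenting for gynecologic surgery at both study areas during the study period will be selected". On when: "with a 1:1 allocation to the treatment group (T) and control group (C) the night before surgery". Section 4.7 gives the participant a sealed envelope to carry to the operating room. It does not say who opens the envelope or at what moment.

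Section 4.4.1 makes consent a condition of entry ("and gave informed consent"). Section 4.4.2 excludes, among others, "those who have preoperative bradycardia, hypotension, or any type of heart block".

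Section 4.10 describes the preoperative steps. Patients "will be assessed and told about the study process and anesthetic the day before the surgery". On the morning of surgery "a separate consent form for the study will be checked and available", and the IV line and NPO status are checked. The baseline instrument comes next, without a stated time: "Standard preoperative questionnaires will be used, and data will be collected through patient responses and medical records". Routine monitoring is applied when the patient reaches the operating room.

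Section 4.12 defines no analysis population. Section 4.13 lets participants withdraw and keeps the data collected while anesthesia was being given.

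**The concern.** The arm is fixed before the last points at which a patient can fall out of the trial. Overnight or in the morning a case may be cancelled, the anesthetic changed, participation withdrawn, or an exclusion such as bradycardia or hypotension discovered. Each such patient already counts as randomised. She has no intraoperative exposure and no postoperative VAS, so in practice she is likely to be dropped or replaced.

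Two things are at stake. The first is loss after randomisation that later allocation would largely have prevented. The second is selective exclusion, if whoever decides that a patient does not proceed can already know her arm. Section 4.7 allows anesthesia providers to know the group. Section 4.10 trains anesthetists involved in patient management to collect data, which sits uneasily with the statement in 4.7 that the anesthetist has no other study role. Without a rule for untreated patients, such exclusions could go unreported, although section 4.13 promises CONSORT reporting.

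**Working it through.** **Order of events**

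| Step | Time given | Section |
|---|---|---|
| Assessment and study information | Day before | 4.10 |
| Consent signed | Not stated; required for entry | 4.4.1 |
| Allocation | Night before | 4.6 |
| Envelope opened | Not stated | 4.7 |
| Study consent form verified | Morning of surgery | 4.10 |
| IV line and NPO status checked | Described next | 4.10 |
| Baseline questionnaire | Not stated; described after those checks | 4.10 |
| Section 4.4.2 exclusions re-checked on the day | Not planned | – |
| Routine monitoring | On arrival in the operating room | 4.10 |
| VAS | PACU discharge, 6, 12 and 24 hours | 4.10 |

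Verification of the form follows allocation by the plan's own wording. Baseline after allocation is an inference from the order of the text. The withdrawal sentence in 4.13 concerns data gathered during anesthesia, so it does not reach a patient who never received any.

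**The sample-size figures this bears on** (section 4.5: z values 1.96 and 0.84, SD 1.9, 31 per group, plus 10%, total 70)

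1. Formula: n = 2 × (1.96 + 0.84)² × SD² / d². Taking a medium effect as 0.5 SD (an assumption, since no number is given), d = 0.95 and n = 2 × 7.84 × 3.61 / 0.9025 = 62.7, that is 63 per group. The stated 31 is not reproduced. That is a separate matter and does not support this point.
2. Difference implied by 31 per group: d = 1.9 × 2.80 × √(2/31) = 1.35 points, or 1.35 / 1.9 = 0.71 SD.
3. The 10% step does reproduce: 31 × 1.1 = 34.1 and 31 / 0.9 = 34.4 both round up to 35 per group, 70 in total. The margin is 70 − 62 = 8 patients, or 8 / 70 = 11.4%.

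**Effect of loss.** The documents give no rate of loss between allocation and induction, so the rates below are assumptions. Power = Φ(√(n/2) × d / 1.9 − 1.96), with n = 35 × (1 − loss), two-sided.

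| Loss | Patients of 70 | n per group | Power, d = 1.35 | Power, d = 0.95 |
|---|---|---|---|---|
| 0% | 0 | 35 | 84.5% | 55.2% |
| 5% | 3.5 | 33.25 | 82.6% | 53.1% |
| 10% | 7.0 | 31.5 | 80.6% | 51.0% |
| 15% | 10.5 | 29.75 | 78.3% | 48.7% |
| 20% | 14.0 | 28 | 75.8% | 46.4% |

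A 15% loss costs about 6 percentage points of power under either difference.

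**The case against.** Allocation the night before in sealed envelopes is not in itself an error, and several stronger readings go beyond the text.

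- A reader might infer that consent is obtained after randomisation. The documents do not say so. The form is verified in the morning, patients are informed the day before, consent is an inclusion criterion, and 4.6 allocates participants already described as eligible. Together these imply consent before allocation. What stands is that the time of signing is not stated.
- A reader might infer a morning fitness check that comes too late. The morning checks named are IV line and NPO status, and monitoring in the operating room is not described as screening. Bradycardia and hypotension could be assessed the day before. What stands is that they can change overnight and no re-check is planned.
- A reader might infer that baseline data are contaminated. The questionnaire has no stated time, participants are not to know their group, and most variables in 4.8.2 can hardly be influenced by allocation. Little of this worry stands.
- A reader might infer that the randomised comparison is broken. If the envelope stays sealed until the operating room, a cancellation on the ward is made without knowledge of the arm and costs numbers without biasing the comparison. What stands is a conditional risk, because the moment of opening is not stated.
- A reader might infer that the allowance will be used up. Section 4.5 already adds 10%. Of the assumed rates up to 15%, only the highest exceeds the 8 spare patients, and power then falls less than two points below 80%.

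**Conclusion.** The point holds as an avoidable weakness of timing together with a missing rule. Section 4.6 fixes the arm before consent verification and the readiness checks. The times of consent signing, baseline completion and envelope opening are not stated, overnight changes in eligibility are not re-checked, and no provision covers a patient allocated but not anesthetised. The consequence is post-randomisation loss that later allocation would mostly prevent, plus a possible bias if the arm is known when a patient is excluded.

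The effect on power is modest: about 4 percentage points at 10% loss and 6 at 15%, taking the 1.35-point difference implied by 31 per group. Those rates are assumptions. The case for change rests on accounting for every randomised patient more than on power. It should be made, but the flaw does not invalidate the design.

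**What to change.** Replace the timing in 4.6: on the day of surgery, just before induction and before any drug that differs by arm, the next sequentially numbered sealed envelope is assigned and opened. The study holds the envelopes at each hospital; participants do not carry them, so 4.7 changes to match. Opening is permitted only once the study consent has been verified, the section 4.4.2 criteria have been re-confirmed that day, and the baseline questionnaire is complete. Screening and the consent discussion stay on the day before.

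In 4.10, state when consent is signed and when the questionnaire is completed. In 4.12, state that all patients so randomised are analysed in their allocated group, and that any randomised but not treated are reported by arm with the reason. The last rule is still needed, because a few patients may be lost between opening and induction.

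The cost is a few sentences in 4.6, 4.7, 4.10 and 4.12, a controlled set of envelopes at both hospitals, and shorter notice of the arm for the anesthesia team. The protocol describes no overnight preparation that depends on knowing the arm, and numbered envelopes kept on site avoid the need for an independent list holder each operating morning.
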